13.6 Reporting and Exclusions

As the nature of this study is exploratory, intent-to-treat should not be used as a principal analysis criterion. Nevertheless, no subjects will be excluded from the analysis and reporting, except for obvious random dropouts and for those who never took the protocol treatment.

Compliance with the protocol treatment will be measured in the form of pill counts, but the information will not be used for the primary analysis. There will be no imputation of missing data for both the primary and the secondary endpoints.

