1. OBJECTIVES

1.1. Primary Objective:

The primary objective of the study is to determine the effect of Pomegranate Fruit Extract (PFE) 1000mg, taken daily for 1 year, on the plasma levels of Insulin-like Growth Factor (IGF-1) from baseline to end of study (52 weeks) in participants undergoing Active Surveillance (AS) for early stage prostate cancer.

1.2. Secondary Objectives:

- 1.2.1. To assess compliance with a once daily oral administration of PFE versus placebo over a 52-week period of time.
- 1.2.2. To assess the toxicity of PFE vs. placebo when taken daily for 52 weeks (+/- 1 week).
- 1.2.3. To compare and correlate the effect of 52 weeks of daily dosing with PFE vs placebo on the end of study biopsy results including the presence or absence of tumor, the extent of tumor and Gleason scores.
- 1.2.4. To compare and correlate biomarker modulation in response to PFE versus placebo in three areas of interest: tissue from a completely benign biopsy core, tumor tissue from a positive core, and normal tissue adjacent to tumor from a positive core. The following biomarkers will be analyzed:
 - Plasma: Insulin-like growth factor 1/IGF binding protein 3 ratio (IGF-1/IGFBP-3 ratio)
 - Prostate tissue (normal and abnormal). In order of priority:
 - apoptosis (CASPASE 3)
 - Ki-67
 - 8OHdG
 - IGF-1R
 - Androgen receptor
 - IGF-1
 - IGFBP-3
 - PSA
- 1.2.5. Measure PFE constituents/metabolites in plasma and urine for evidence of accumulation (trough levels): ellagic acid, dimethyl ellagic acid, dimethyl ellagic acid glucuronide (DMEAG), urolithin A, urolithin A-glucuronide, urolithin B and urolithin B-glucuronide.
- 1.2.6. Measure PSA doubling time (PSA DT) in serum, using the calculation provided on the Memorial Sloan Kettering Cancer Center website: nomograms.mskcc.org/prostate/psadoublingtime.aspx
- 1.2.7. To assess the feasibility of cancer chemoprevention trials in a population of men undergoing active surveillance for prostate cancer.

1.2.8. Measurement of serum testosterone.

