8. CRITERIA FOR EVALUATION AND ENDPOINT DEFINITION

8.1 Primary Endpoint

The primary endpoint of the study is change in plasma IGF-1 from baseline to end of study (12 months).

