13. STATISTICAL CONSIDERATIONS

13.1 Study Design/Endpoints

This is a Phase IIA randomized, placebo-controlled, double-blind trial of modulation of intermediate endpoint biomarkers by PFE as POMx™ in subjects undergoing AS for low grade, early stage prostate cancer for 12 months. Participants will be randomized to placebo or PFE as POMx™ given for 12 months in a 1:1 ratio stratified by tumor volume.

The primary endpoint for modulation of intermediate endpoint biomarkers will be the change in the plasma levels of IGF-1 by a quantitative assay (ELISA) from pre-study to post-treatment.

The secondary endpoints include compliance and toxicity over the study duration, plasma biomarkers such as IGFBP-3, IGF-1/IGFBP-3 ratio, total PSA (serum), tissue (normal, normal adjacent to tumor, and abnormal prostate) biomarkers such as PSA, IGF-1, IGFBP-3, apoptosis (CASPASE 3), Ki-67, IGF-1R, 80HdG, and AR. Also, the following PFE constituents/metabolites will be measured for evidence of accumulation (trough levels): ellagic acid, dimethyl ellagic acid, dimethyl ellagic acid glucuronide (DMEAG), urolithin A, urolithin A glucuronide, urolithin B and urolithin B glucuronide.

The primary analysis will be a comparison of change in IGF-1 plasma levels from pre-study to post-study, based on two-sample t-test with normalizing transformation if necessary or Wilcoxon rank-sum test.

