13.8 Evaluation of Response

For the primary analysis comparing the change in the IGF-1/IGFBP-3 ratio from pre-study to post-study biopsies, the as-treated analysis will be used. All of the participants who met the eligibility criteria, with the exception of those who did not receive study agent, will be included in the main analysis. Random dropouts will be excluded.

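### Section 13.8 misnames the primary endpoint and describes the analysis set differently from 13.6; 'random dropout', the 80% rule and one group's IGF-1 sample also need settling

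*Combined protocol and SAP*

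**What the plan says.** **Endpoint.** Section 8.1 reads: "The primary endpoint of the study is change in plasma IGF-1 from baseline to end of study (12 months"). Sections 1.1, 13.1 and 13.4 agree, and 13.2 sizes the trial on change in IGF-1. The ratio appears as a secondary plasma measure in 1.2.4 and 13.5, and in 13.1 among "plasma biomarkers such as IGFBP-3, IGF-1/IGFBP-3 ratio". Section 13.8 stands apart: "For the primary analysis comparing the change in the IGF-1/IGFBP-3 ratio from pre-study to post-study biopsies, the as-treated analysis will be used".

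**Analysis set.** Section 13.6 first says that intent-to-treat should not be the principal criterion in an exploratory study, then that "no subjects will be excluded from the analysis and reporting, except for obvious random dropouts and for those who never took the protocol treatment". It adds that pill counts do not enter the primary analysis and that missing data are not imputed. Section 13.8 takes into the main analysis "All of the participants who met the eligibility criteria, with the exception of those who did not receive study agent", and adds: "Random dropouts will be excluded".

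**Compliance.** Sections 5.7.1 and 7.3.1.5 make at least 80% compliance a condition of being evaluable, without naming an analysis that uses it.

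**Early stoppers.** Section 7.4 places the final visit at week 52 or at the end of therapy, whichever is earlier. Section 5.6 lets men who stop drug permanently for an adverse event stay on the visit schedule. Section 3 asks for all end-of-study assessments from men who leave for surgery. Section 8.2 says which value counts for PSA doubling time; no equivalent rule exists for IGF-1.

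**The concern.** Section 13.8 is the paragraph that says who enters the main analysis. Followed literally, it would test a secondary variable, in the wrong specimen, as the primary result.

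The set is also left partly to judgement. With 30 men and no imputation, keeping or dropping one or two can move the result. If that choice, or the choice between two candidate IGF-1 samples, is made after the treatment code is known, it can follow the data.

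**Working it through.** **1. The plan's own figure.** Inputs from 13.2: two-sided alpha 0.05, two-sample t-test, 14 per group, effect 1.10 SD (power 0.80) or 1.17 SD (power 0.85), dropout up to 5%.

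Power is the probability that a noncentral t variable with 2n − 2 degrees of freedom and noncentrality d√(n/2) exceeds the critical value.
- d = 1.10, n = 14: noncentrality 1.10 × √7 = 2.91, power 0.800.
- d = 1.17, n = 14: noncentrality 1.17 × √7 = 3.10, power 0.846.
- Enrolment: 14 / 0.95 = 14.7, so 15 per group.

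The sample size reproduces, and the point does not depend on it. At d = 1.10, power is 0.828 with 15 per group, 0.800 with 14, 0.768 with 13 and 0.731 with 12.

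**2. Sections 13.6 and 13.8 side by side.**

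| Element | 13.6 | 13.8 |
|---|---|---|
| Variable | not named | IGF-1/IGFBP-3 ratio, biopsies |
| Never treated | excluded | excluded |
| Random dropouts | excluded if obvious | excluded |
| Eligibility condition | none | must have met criteria |
| Label | intent-to-treat not principal | as-treated |
| Compliance | not used | not mentioned |

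The two agree on both exclusions. They differ in the eligibility condition and the label. Ineligibility can surface after entry (8.4 lists it as an off-study reason), but central review before randomisation (6.8, 7.2.10) should make that rare.

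**3. How often a doubtful case could arise.** The protocol's five-year figures for progression or elective intervention are 40–50% (2.1) and 20–30% plus 10–20%, that is 30–50% (2.3). At constant hazard (assumption), the annual rate is 1 − (1 − p)^(1/5).
- p = 0.30: 6.9% per year, 30 × 0.069 = 2.1 men, probability of at least one 0.88.
- p = 0.50: 12.9% per year, 30 × 0.129 = 3.9 men, probability 0.98.
- If only half stop before week 52 (assumption): 1.0 to 1.9 men, probability 0.65 to 0.87.

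These are men who might stop early. The documents do not say that they would be excluded.

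**4. Bias if some are excluded.** Simulation with no true effect, 15 per arm, 200,000 runs, pooled t-test. The 1, 2 or 3 men removed are those most extreme on a variable with correlation r to the outcome. Both r and the numbers removed are assumptions.
- One arm only, r = 0.25: shift 0.03 / 0.06 / 0.08 SD, type I error 0.051 / 0.054 / 0.056.
- One arm only, r = 0.5: shift 0.06 / 0.12 / 0.16 SD, type I error 0.055 / 0.062 / 0.072.
- Both arms equally, r = 0.5: no shift, type I error about 0.054 to 0.056.
- Removal unrelated to outcome: type I error about 0.05.

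**5. Choice of sample.** True effect 1.10 SD, 15 per arm, with 1, 2 or 3 men on active treatment stopping early (assumption).
- End-of-therapy value carrying the full effect: 1.10 SD, power 0.83.
- Week-52 value, effect wholly lost: 1.03 / 0.95 / 0.88 SD, power 0.76 / 0.69 / 0.60.
- Week-52 value, half the effect lost: power 0.80 / 0.77 / 0.74.

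Section 6.2 gives gastrointestinal events in under 2% at 1000 mg. If these were the only cause, at a 2% rate among 15 men, the chance of at least one stopper is 0.26 and of two or more 0.035.

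**6. The 80% rule.** Section 7.3.1.5 computes compliance by visit period. A man taking 72 of 91 capsules in one period is at 79.1% there. If he takes all 273 in the other three, he is at (72 + 273) / 364 = 94.8% overall. Whether he is evaluable depends on an unstated choice, but under 13.6 it cannot change the primary result.

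**The case against.** The plan can be read sensibly. Five sections point to plasma IGF-1, and a plasma ratio cannot come from biopsies, so 13.8 looks like a lone slip. The exclusions in 13.6 and 13.8 match, and 13.6 limits dropouts to obvious ones. A man who leaves for surgery and supplies the requested blood is not naturally a random dropout, and a man without an end sample drops out of the analysis anyway. Section 13.6 settles compliance for the primary analysis. The final column of the 7.1 schedule, 7.4 and the post-treatment wording in 13.1 lean towards the end-of-therapy sample.

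Much of this stands, and it rules out stronger readings that a reader might infer:
- That the primary endpoint cannot be identified. It can; 13.8 is the outlier.
- That low compliers are removed from the primary analysis. Section 13.6 rules this out.
- That men will be regrouped by the product they took. No section does so, despite the as-treated label.
- That the off-study reasons in 8.4 define the analysis set. They act only through missing outcomes.
- That the sample is open for every early stopper. For men who leave at the end of therapy it is specified.
- That material bias is likely. The blind (6.9) and shipment of research samples only after a man finishes (3, 10.3) mean that his IGF-1 cannot guide his own stopping.

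The objection does not remove the wrong statement in 13.8, define random dropout, give the 80% rule a purpose, or choose between two samples for men who continue under 5.6. Section 8.1 sets the endpoint at 12 months, against the lean towards end of therapy.

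**Conclusion.** The point holds in a limited form and should be fixed. Section 13.8 is wrong as written on variable and specimen. Its set differs from 13.6 narrowly, in the eligibility condition and the label. The undefined dropout exclusion, the unattached 80% rule and the open IGF-1 sample are real gaps of limited reach.

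The likely bias is small. The largest figure, a type I error of 0.072, needs three of 15 men removed from one arm only with correlation 0.5, and the documents support neither. The loss of power is 0.83 to 0.76 for one stopper whose effect is wholly lost, and about 0.80 if half is lost; 0.80 is also the planned power at 14 per group. The 0.69 and 0.60 results need two or three such men, which is unlikely if gastrointestinal events are the only cause. Confidence is high on the textual conflicts and low on how many men they will affect.

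**What to change.** - In 13.8, name change in plasma IGF-1 as the primary endpoint.
- State one primary set, once, for both sections: all treated randomised men with baseline and end-of-study plasma IGF-1, in the arm assigned, regardless of compliance or reason for stopping. This replaces the as-treated label, the separate eligibility condition and the random-dropout exclusion. It is a complete-case set without never-treated men, so it respects 13.6's position on intent-to-treat.
- Record who is in the set before the treatment code is opened.
- State that the 80% rule does not govern the primary analysis.
- Reconcile 5.6, 7.4 and 8.1, and name in advance which IGF-1 sample counts for men who stop early, with the other as a sensitivity analysis. Which is primary is the sponsor's choice.

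The cost is revised wording and one extra analysis on samples already planned. If off-treatment values are chosen, the effect is somewhat diluted. The set remains complete-case, so missing outcomes are still not addressed.

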13.7 Evaluation of Toxicity

All participants receiving any protocol treatment will be evaluated for toxicity from the time of their first dose of placebo or PFE up to the time of biopsy according to the NCI's Common Terminology Criteria for Adverse Events (CTCAE) version 4.0.

13.8 Evaluation of Response

For the primary analysis comparing the change in the IGF-1/IGFBP-3 ratio from pre-study to post-study biopsies, the as-treated analysis will be used. All of the participants who met the eligibility criteria, with the exception of those who did not receive study agent, will be included in the main analysis. Random dropouts will be excluded.

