13.2 Sample Size/Accrual Rate

The sample size for each group is based on comparing the change in IGF-1 levels between the PFE and placebo arms. According to ELISA assay analysis, this primary endpoint can be considered a continuous random variable. The sample size justification is thus based on a two-tailed two-sample t-test of the difference between the two groups at a significance level of 0.05. In order to detect an effect size of 1.10, i.e. the difference in the mean change between the two groups of 1.10 standard deviations, with power 0.80, or an effect size of 1.17 with power 0.85, the trial requires an effective sample size of 14 per group. Assuming a random dropout of up to 5%, 15 subjects per group will be enrolled for a total of 30 subjects for this exploratory study.

There will be six organizations participating in the study. With each PO randomizing one participant per month, a conservative estimate, the study will enroll the target accrual goal of 30 subjects within 6 months. Considering the usual delay due to start-up, it may take up to 18 months. Each randomized participant will be treated with study medication for one year. We will allow for a study duration of two-three years.

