13.4 Primary Endpoint(s)

The primary endpoint of the study is the difference in plasma levels of Insulin-like Growth Factor (IGF)-1 from baseline to end of study (12 months) in subjects undergoing AS for early stage prostate cancer. For the primary comparison, the difference between the placebo group and the PFE group will be tested using a two-sample t-test with normalizing transformation if necessary or Wilcoxon rank-sum test.

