13.5 Secondary Objectives

For the secondary objectives, we will compare compliance and toxicities for a once daily oral administration over a 12-month period of time between the PFE and placebo groups. We will compare the modulation of the following biomarkers with response to PFE versus placebo: plasma biomarkers, including IGF-1/IGFBP-3 ratio, total serum PSA and normal and abnormal prostate tissue biomarkers, including PSA, IGFBP-3, apoptosis (CASPASE 3), Ki-67, IGF-1R, 8OHdG and androgen receptor. We will also compare PFE constituents/metabolites for evidence of accumulation (trough levels): ellagic acid, dimethyl ellagic acid, dimethyl ellagic acid glucuronide (DMEAG), urolithin A, urolithin A glucuronide, urolithin B and urolithin B glucuronide between the treatment groups. Serum testosterone levels will also be measured.

For secondary objectives, all measurements and changes in measurements of interest will be summarized by treatment arm (and, if applicable, by visit) with appropriate descriptive statistics. Compliance, in terms of the number of pills missed, will be summarized by treatment arm with descriptive statistics, and tested for imbalance using Wilcoxon rank-sum test. Patient toxicity throughout the study will be summarized in several ways; the presence or absence of any toxicities, worst CTCAE grade, and strongest investigator-defined relationship will all be examined and characterized by treatment arm, and analyzed appropriately (Wilcoxon rank-sum for ordinal data, Fisher's exact test for dichotomous data, and log rank test for time to event data). We will examine the differences between the groups for the change from baseline for serum biomarkers, tissue biomarkers, and PFE constituents/metabolites with the appropriate tests; for dichotomous data we will use Fisher's exact test, for ordinal data we will use Wilcoxon rank-sum test, and for continuous data, and a two-sample t-test with normalizing transformation if necessary or Wilcoxon rank-sum test.

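### Section 13.8 names the change in the IGF-1/IGFBP-3 ratio between biopsies as the primary analysis, while the endpoint, analysis and sample-size sections name plasma IGF-1

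*Combined protocol and SAP*

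**What the plan says.** The primary variable is stated in several places, and all but one agree. Section 1.1 sets the primary objective as the effect on plasma IGF-1 over 52 weeks. Section 8.1 defines the primary endpoint as the change in plasma IGF-1 over the study, and 13.4 repeats this with the test to be used. Section 13.1 says the primary endpoint "will be the change in the plasma levels of IGF-1 by a quantitative assay (ELISA) from pre-study to post-treatment", and adds: "The primary analysis will be a comparison of change in IGF-1 plasma levels from pre-study to post-study". Section 13.2 states: "The sample size for each group is based on comparing the change in IGF-1 levels between the PFE and placebo arms".

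The IGF-1/IGFBP-3 ratio has a secondary role in three places: the plasma list in 1.2.4, the secondary endpoints in 13.1, and 13.5, which compares "plasma biomarkers, including IGF-1/IGFBP-3 ratio".

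Section 13.8 is the exception: "For the primary analysis comparing the change in the IGF-1/IGFBP-3 ratio from pre-study to post-study biopsies, the as-treated analysis will be used". The same section then restricts the main analysis to eligible participants who received study agent and removes random dropouts.

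**The concern.** A single pre-specified test controls the type I error only if the plan identifies one variable. Read as written, 13.8 departs from the other sections in three ways:

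- **Analyte:** a ratio of two proteins instead of IGF-1.
- **Specimen:** biopsies instead of plasma.
- **Baseline:** a pre-study biopsy that may be up to 13 months older than the baseline visit (7.1, footnote 5), instead of the baseline blood draw.

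With two candidates in the statistical section, a result on either could be presented as primary after the data are seen, and a result on either could be challenged. A biopsy-based primary would also depend on usable tissue at both time points.

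The sentence has a further effect. Section 13.8 is the only place that calls the analysis as-treated and requires that eligibility criteria were met. Section 13.6 excludes only random dropouts and men who never took treatment. Because 13.8 ties its rule to the ratio, it is unclear which population rule governs plasma IGF-1.

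**Working it through.** **1. The sections side by side**

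| Section | Role | Variable | Specimen |
|---|---|---|---|
| 1.1 | Primary objective | IGF-1 | Plasma |
| 8.1 | Primary endpoint | Change in IGF-1 | Plasma |
| 13.1 | Primary endpoint and primary analysis | Change in IGF-1 | Plasma (ELISA) |
| 13.2 | Sample size | Change in IGF-1 | ELISA; plasma not repeated |
| 13.4 | Primary endpoint and test | Difference in IGF-1 over 12 months | Plasma |
| 13.8 | Primary analysis | Change in IGF-1/IGFBP-3 ratio | Biopsies |

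Section 13.2 omits the word plasma, but its reference to the ELISA ties it to the endpoint in 13.1. No section supports 13.8.

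**2. Is the 13.8 variable defined elsewhere?** It is not. The ratio appears only as a plasma marker (1.2.4, 13.1, 13.5). Tissue IGF-1 and IGFBP-3 are separate immunohistochemistry markers read in three regions: benign, normal adjacent to tumor, and tumor (1.2.4, 9.1). The plan gives no tissue ratio and no choice of region for one. In the tissue priority list of 1.2.4, IGF-1 is sixth and IGFBP-3 seventh of eight. Section 10.2 allows for insufficient tissue and 13.6 rules out imputation, so these markers would be among the more exposed to missing data.

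**3. Reproducing the sample size.** Inputs from 13.2: two-sided alpha 0.05, two-sample t-test, 14 per group, effects of 1.10 and 1.17 SD, dropout up to 5%. Degrees of freedom are 2 × 14 − 2 = 26, and the noncentrality parameter is d × √(n/2).

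- d = 1.10: 1.10 × √7 = 2.91, power 0.7999 (stated 0.80).
- d = 1.17: 1.17 × √7 = 3.10, power 0.846 (stated 0.85).
- Dropout: 14 / 0.95 = 14.7, rounded up to 15 per group, 30 in total.

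The stated figures are sound. They are given for change in IGF-1.

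**4. Power for the ratio.** The documents give no expected effect for it. If its standardized effect were 0.8, 1.0 or 1.2 (assumed values), power at 14 per group would be 0.53, 0.72 or 0.86.

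**5. Error rate if either variable may be called primary.** Assume both are tested at 0.05 and one significant result is enough. With independent tests the rate is 1 − (1 − 0.05)² = 0.0975. For correlated variables, simulated t-tests at 14 per group give approximately:

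| Correlation (assumed) | P(at least one p < 0.05) |
|---|---|
| 0 | 0.0975 (exact) |
| 0.3 | 0.095 |
| 0.5 | 0.09 |
| 0.7 | 0.084 |
| 0.9 | 0.07 |

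**The case against.** The best defense is that the intended hierarchy can be recovered. The sections whose job is to define the endpoint, 8.1 and 13.4, say plasma IGF-1. So does the explicit statement of the primary analysis in 13.1, and the ratio is secondary in three places. On this view 13.8 is one stray sentence in a paragraph about the analysis population. That is probably how it arose, but the origin cannot be shown from the documents. Counting sections is also not pre-specification, and 13.8 carries an operative rule for the primary analysis.

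The reference to biopsies might mark time points and not the specimen, since the final blood draw and biopsy belong to the same visit. That reading is possible. However, 8.2 describes plasma as compared from baseline to end of study and tissue as compared from biopsy to biopsy, and 13.8 uses the biopsy form. Even on the milder reading, the analyte is still wrong.

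Two objections to the size stand in part. First, the error rates are conditional. They need both variables to be tested and either to be reportable, and zero correlation is implausible if the ratio is the plasma one, because IGF-1 is its numerator. Second, 13.2 works only in SD units and gives no SD for IGF-1 either, so its arithmetic would serve any continuous change score with a 1.10 SD effect. What is missing is any reason to expect that effect on a biopsy ratio.

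Finally, the plan calls itself exploratory (13.2, 13.6) and a pilot (8.2), which lowers the stakes for alpha. It still specifies one primary comparison, sized at a two-sided 0.05, and the variable for it must be unambiguous.

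**Conclusion.** The concern holds. Section 13.8 contradicts five sections on the identity of the primary variable, and nothing in the plan resolves it. The mismatch in analyte is certain. The mismatch in specimen and baseline follows from the literal wording.

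The sample size is correct for IGF-1 and is not in question. If the ambiguity were exploited, a nominal 5% error rate would become roughly 7% to 9.75% over correlations from 0.9 to 0. That is a conditional illustration and not a prediction of what the sponsor would do. This must be fixed because it concerns which test is primary and which population rule applies to it.

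**What to change.** Reword the opening of 13.8 so that the as-treated rule attaches to the comparison of change in plasma IGF-1 between baseline and end of study (week 52). Using end of study keeps the wording in line with 8.1 and covers men whose final visit comes early. State in the same section that the plasma IGF-1/IGFBP-3 ratio and the tissue IGF-1 and IGFBP-3 measures are secondary. While the section is open, align its eligibility condition with 13.6 so that one population rule governs the primary analysis.

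The change should be made before unblinding. It costs one sentence of protocol text plus that alignment. The sample size stays at 14 evaluable and 15 enrolled per group, with no new data and no new participants.
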